## 6.0 DATA AND SPECIMEN SUBMISSION

### 6.1 Medidata Rave®

This study will use Medidata Rave® for remote data capture (RDC) of all study data. The Rave system can be accessed through the iMedidata portal at <https://login.imedidata.com>. For additional information regarding account setup or training, please visit the training section of the Alliance Web site. Copies of forms and a data submission schedule are also available for download at the Alliance Web site.

Common Terminology Criteria for Adverse Events: This study will utilize the Common Terminology Criteria for Adverse Events (CTCAE) version 4.0 for toxicity and adverse event reporting.

### 6.2 A091105-HO1 (QOL) data submission

QOL booklet ordering instructions can be found in [Appendix II](#). For patients who consent to model consent question #1, the assessments in the table below are to be completed at the following timepoints:

| Assessment                      | Within 28 days prior to randomization | Within 28 days prior to treatment | Weeks 4, 8, 12, 16, 20, 24, 28, and 32 of treatment (+/- 3 days)
(i.e. Cycles 1-8, Days 22-28) | End of randomized treatment |
|---------------------------------|---------------------------------------|-----------------------------------|---------------------------------------------------------------------------------------------------|-----------------------------|
| Brief Pain Inventory Short Form | X                                     |                                   | X                                                                                                 | X                           |
| PRO-CTCAE                       | X                                     |                                   | X                                                                                                 | X                           |
| Single-item overall LASA        | X                                     |                                   | X                                                                                                 | X                           |
| Pain Medication Diary           |                                       | X*                                | X                                                                                                 | X                           |

\* Daily reporting for 7 consecutive days via paper diary prior to treatment. Pain medication diary is not found in QOL booklet.

The Brief Pain Inventory Short Form, PRO-CTCAE and Single-item overall LASA are all contained with the QOL questionnaire booklets (see [Appendix II](#)). **Samples of QOL questionnaires found in Appendix II of the protocol document are for reference and IRB submission only. They are not to be used for patient completion.**

The pain medication diary is not part of the QOL Booklet and must be printed. The pain medication diary should be completed during treatment weeks 4, 8, 12, 16, 20, 24, 28, and

32 weeks. Therefore, since a cycle is 28 days, the pain medication diary should be completed the last week of each cycle.

On Day 1 of each cycle site staff should prepare the pain medication diary by listing the pain medication names, routes and strengths in the appropriate columns on the pain medication diary. Site staff must then send the partially completed diary home with the patient and ask that they complete it for the 7 days leading up to the next appointment.

The QOL assessments cannot be translated, therefore, only English-speaking patients may enroll on this substudy.

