**SCHEMA**  
**1 Cycle = 28 Days**

PD= Progression of Disease

\* Patients are unblinded after first incidence of progressive disease

NOTE: Patients discontinuing for reasons other than PD and earlier than 1 year post-randomization must continue in Clinical Follow-up until 1 year post-randomization to capture study endpoints.

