- \* Pre-registration labs may be used for day 1 of cycle 1 tests if obtained within 28 days prior to day 1 of Cycle 1.
- \*\* For patients discontinuing treatment for reasons other than progressive disease (PD) and prior to 1 year post-randomization, Clinical Follow-up continues at least every 8 weeks after discontinuing treatment until the earliest PD or until 1 year after randomization. Patients on the placebo arm may cross over to the sorafenib arm upon PD, and continue in Clinical Follow-Up. Treatment with sorafenib after crossover must begin within 28 days following documentation of progression.
- \*\*\* After progression on sorafenib, patient will be followed per. [Section 14.1](#)
- † For patients who consent to A091105-ST1. Not required for patients who have crossed over to sorafenib.
- 1 To be performed only for patients with palpable disease. Submit measurements in cm with two dimensions.
- 2 To be completed within 21 days prior to registration, see Appendix I.
- 3 Within 28 days prior to randomization, every 4 weeks up to Week 32 while on randomized treatment, and at the end of randomized treatment; see [Section 6.2](#). These items are not required after patients have crossed over to sorafenib.
- 4 For women of child bearing potential. To be obtained within 3 days prior to day 1 of Cycle 1, **and** after crossover, ≤ 7 days prior to starting treatment with sorafenib.
- 5 Required for all patients registered to A091105 and will be used for confirmation of diagnosis as described in [Section 6.3.1](#). For patients who consent to A091105-ST1, this tissue block will also be used for study described in [Section 10.3](#).

- 6 Must be completed within 28 days of registration. Patients who consent to A091105-HO1 will meet this requirement by answering question #1 on baseline QOL assessment (see [Appendix II](#)). For patients who do not consent to A091105-HO1, see [Appendix V](#).
- 7 All MRI images are to be submitted to the Alliance ICL per [Section 6.4](#) and will be analyzed as described in [Section 10.1](#)

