• **Pain Medication Diary:** Daily reporting for 7 consecutive days via paper diary prior to randomization, every 4 weeks through Week 32 while on randomized treatment, and at end of randomized treatment. This pain medication diary will be used to quantify opioid narcotic use for computing pain palliation and pain progression.

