#### **Unblinding procedures upon progression**

CROSSOVER (open label sorafenib) THERAPY (Placebo Arm Only)

1. Site physician deems that the patient has had radiographic or clinical progression.
2. Site staff contacts the Alliance Registration Office at [contact] during regular business hours for treatment assignment.
3. If patient was on placebo, site may offer crossover to the patient.
4. Site must enter data within 14 days of unblinding for quality assurance purposes.
5. Site re-registers patient in OPEN (See Section 5.5 for re-registration instructions)
6. Alliance SDC orders drug and site receives open label drug from the Protocol Management Branch (See [Section 11.2.2](#)).

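### End-of-randomized-treatment pain and quality-of-life reports can be made after the arm is known, and the HO1 analysis plan neither censors nor flags them

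*Combined protocol and SAP*

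**What the plan says.** **Collection.** The table in Section 6.2 lists the pain inventory, PRO-CTCAE, LASA and pain diary at baseline, at Weeks 4 to 32 with a window of 3 days either side, and at "End of randomized treatment", which has no window. The study calendar in Section 7.0 repeats the schedule: "Within 28 days prior to randomization, every 4 weeks up to Week 32 while on randomized treatment, and at the end of randomized treatment". Its only limit on late completion is "These items are not required after patients have crossed over to sorafenib". Section 10.2.2 sets the diary "every 4 weeks through Week 32 while on randomized treatment, and at end of randomized treatment".

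**Unblinding.** The schema states "Patients are unblinded after first incidence of progressive disease", and Section 5.5 says the same for confirmed progression, without restricting it to one arm. Section 14.1 continues treatment until progression or unacceptable adverse events. In Section 11.2.6 the site physician declares progression, staff contact the registration office "during regular business hours for treatment assignment", and a placebo patient may then be offered crossover. No questionnaire step precedes the contact.

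**Analysis.** Section 15.3.2 dates pain progression at the earliest observed report that meets the definition and censors other patients at their last pain report. Duration of palliation ends at the same event. Each patient-reported outcome is compared between arms at each time point. Nothing refers to unblinding at progression. The note opening Section 15.2 concerns crossover treatment linked to the unblinding of November 17, 2017. Sections 15.3.1 and 15.3.3 cite that note; Section 15.3.2 does not.

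**The concern.** Worst pain, opioid use and overall quality of life are all reported by the patient. Someone who has just learned that they were on placebo and may now receive sorafenib, or that their tumour grew on sorafenib, may answer differently from someone still blinded. The two messages differ by arm, so the effects need not cancel.

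The end-of-treatment report can change the result for an individual. In a patient without earlier pain progression, it either supplies the event or becomes the censoring date. Section 10.2.3 makes time to pain progression the secondary hypothesis of HO1, and Section 10.2 gives patient-reported outcomes a prominent place among the secondary endpoints. The comparison would be presented as coming from a double-blind trial although some of its reports may not be blinded.

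The 2017 unblinding adds a second route: a patient still on randomized treatment on that date can only give a later end-of-treatment report with the arm known.

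**Working it through.** The question is mainly one of sequence, so the passages come first and the arithmetic only sizes the exposure. The plan states no figure on this point to reproduce.

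**Sequence**

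1. Progression ends randomized treatment (14.1), so the end-of-treatment reports fall due (6.2, 7.0).
2. The same event unblinds the patient in either arm (schema, 5.5).
3. The steps in 11.2.6 run from declaring progression straight to the request for the assignment.
4. The only stop is crossover. Section 7.0 allows up to 28 days from documented progression to the start of crossover sorafenib. Sorafenib patients, and placebo patients who do not cross over, have no stated limit.
5. The recall periods are short. The worst-pain item covers the last 24 hours (Appendix V), and each diary entry covers the prior 24 hours. A worst-pain answer given a full day after the call describes only unblinded time.
6. Section 15.3.2 has no rule that separates such reports.

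**What is not exposed**

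- The HO1 primary endpoint uses Weeks 8 and 12 only, and missing data count as non-response.
- Scheduled Week 4 to 32 reports made on randomized treatment come before unblinding at progression.
- Patients who stop for toxicity without progression are not unblinded at that point (11.2.6), so their end-of-treatment forms fall due while still blinded.

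**Exposure**

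Inputs: median PFS of 6 months on placebo and 15 months on sorafenib (15.1.1); 51 patients in the HO1 primary analysis with 2:1 randomization (15.3.2), so 17 and 34. Assumption: exponential PFS.

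P(event by t) = 1 − 2^(−t/median), with t = weeks × 7 / 30.4375 months.

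| Time | t (months) | Placebo | Sorafenib | Of 17 | Of 34 |
|---|---|---|---|---|---|
| Week 12 | 2.76 | 27% | 12% | 4.6 | 4.1 |
| Week 32 | 7.36 | 57% | 29% | 9.7 | 9.8 |
| Week 52 | 11.96 | 75% | 42% | 12.7 | 14.4 |

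For Week 32: 1 − 2^(−7.36/6) = 0.573 and 1 − 2^(−7.36/15) = 0.288.

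Under these assumptions each row is an upper bound on exposure by that time. PFS events include deaths, and some forms will have been completed before the call. By Week 32 the proportion exposed is about twice as high on placebo (0.573 / 0.288 = 2.0). The 51 patients are those with baseline pain of at least 3 who meet the other conditions of the primary HO1 analysis. Section 15.3.2 drops the pain requirement for the other questionnaires, so those denominators may differ.

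**The case against.** The case on the other side is substantial, and much of it stands.

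- **Completion after unblinding is possible, not certain.** A booklet filled in at the progression visit before the call stays blinded. Part of the questionnaire appendix was not available for this check, and Section 6.1 refers to a data submission schedule held elsewhere. Either might contain a timing instruction.
- **Blinded data often exist close to progression.** Through Week 32, scans fall on Day 1 of cycles 3, 5, 7 and so on, within 7 days, and reports fall on Days 22 to 28 of cycles 1 to 8. The Week 8, 16, 24 and 32 reports therefore sit near the scans. This reduces the problem but does not remove it, because the end-of-treatment report is still collected and can still supply an event.
- **The affected endpoints are not the main ones.** Section 15.3.2 labels the time-to-event pain analyses exploratory.
- **Datasets are shared.** Section 10.2.3 says HO1 will use the clinical analysis datasets for consistent censoring and handling of crossover data. That does not clearly reach a report made after unblinding and before crossover, or one from a sorafenib patient.
- **The blinded phase is essentially over.** A new collection step will reach few or no patients. The analysis rule still matters.

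Four stronger readings are tempting, and the documents do not support them.

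- A reader might infer that all 52 planned PFS events in 75 patients are exposed. HO1 is optional and limited to English speakers, and PFS events include deaths.
- A reader might infer that after Week 32 the 7-day diary can start only once progression is known. Section 6.2 also has staff prepare a diary on Day 1 of each cycle and "ask that they complete it for the 7 days leading up to the next appointment", which can be read as continuing beyond cycle 8.
- A reader might infer that these reports feed the mixed model. That model uses the planned week of assessment, and end of treatment has no planned week, so their entry is unclear.
- A reader might infer that most pain progression events will be recorded at this visit. Up to eight scheduled reports may precede it, and nothing in the documents shows how events would divide between them.

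**Conclusion.** The point holds in a limited form. The documents permit end-of-randomized-treatment self-reports to be made after the arm is known, and Section 15.3.2 lets them count in time to pain progression, duration of palliation and end-of-treatment comparisons without separating them. The tempting wider conclusion, that the trial's patient-reported outcomes as a whole lose the blind, does not follow: the HO1 primary endpoint and the scheduled reports made before progression are unaffected.

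The number of reports open to the problem by Week 32 is at most about 10 per arm in HO1. That figure rests on exponential PFS at the design medians and a 17:34 split, and later progressions add to it. The documents give no pain means, variances or response shifts, so neither the size nor the direction of a bias can be derived. This is a cheap improvement to secondary and exploratory results and has no consequence for sample size.

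**What to change.** **Sections 6.2 and 11.2.6.** For any patient still blinded, require the end-of-treatment booklet and the preceding 7 days of opioid use to be completed and dated before the call for the assignment.

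**Section 15.3.2.** From recorded dates, classify every report as before or after unblinding, whether at progression or on November 17, 2017. Pre-specify an analysis of time to pain progression, duration of palliation and the end-of-treatment comparisons that censors at unblinding or excludes reports made after it. Show it beside the analysis of all reports. State whether end-of-treatment reports enter the mixed model and, if so, at what time value.

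**Cost.** The collection step needs little time at a visit the patient already attends, and may now apply to few or no patients. The analysis needs existing dates and a little programming. The restricted version has its own weakness: it loses reports at progression, which the design expects earlier on placebo, so the loss is related to outcome and differs by arm. Neither version should be read alone; agreement between them is the reassurance sought.

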### 6.3 Specimen Submission

| Specimen                                     | Baseline  | Cycle 1, Day 8
(+7 days) | Location |
|----------------------------------------------|-----------------------|-----------------------------|----------|
| Archival tissue block
(FFPE)  | X                     |                             | OSU      |
| Peripheral whole
blood        | X                     | X                           | OSU      |
| Research tumor
biopsy         | X                     | X                           | OSU      |
| Plasma                           | X                     | X                           | OSU      |

1 Required for all patients registered to A091105. For patients who consent to A091105-ST1, this tissue block will also be used for study described in [Section 10.3](#)

2 For patients consenting to optional study A091105-ST1

3 Obtain prior to the start of protocol treatment and between days 8 and 11 of Cycle 1

#### 6.3.1 Formalin Fixed, Paraffin Embedded (FFPE) Tissue

Archival Tissue: All patients must submit an archival tumor specimen block for required retrospective pathology review. This block will be used by the study pathologist to confirm diagnosis of desmoid tumor (DT/DF). For patients who consent to A091105-ST1, this tissue block will also be used for the study described in [Section 10.3](#).

At least 1 adequate-sized archival paraffin block(s) representative of the primary tumor from a diagnostic or therapeutic procedure at time initial diagnosis or subsequently, should be retrieved from the surgical pathology department. Blocks which contain minimal amounts of tissue specimen (less than 0.5 cm^2 on the block face) or that are very thin (less than 0.5 cm in depth) should not be submitted unless the block is the only representative tissue for the case. A de-identified surgical pathology report should be sent with all blocks. Usually, this is generated by obscuring all PHI (names and dates) with white-out or a black magic marker, labeling each page of the report with the Alliance patient ID, and photocopying the report.

Paraffin blocks retrieved from the surgical pathology department should have a label affixed to them that includes the protocol number, Alliance patient ID, and patient initials. The surgical pathology case number and block identifier should be maintained on the report so that it can be matched with the physical labeling on the block. Paraffin blocks should be shipped within 30 days of starting protocol treatment to Alliance Biorepository at Ohio State (OSU). Upon receipt at OSU, representative H&E slides and/or scanned images will be provided to designated study pathologist for retrospective pathology review. The

pathologist and/or study chair will request block shipping periodically (approximately every 4 months). All blocks will be held by the appropriate Alliance biorepository but will be returned within 30 days of a written request.

**In instances where a tissue block cannot be released due to institutional or governmental policy**, please contact the Alliance OSU to obtain information about submission of tissue sections as an alternate specimen.

Archival blocks should be requested at time of consent. Blocks should be shipped overnight to Alliance OSU.

### **6.3.2 Research frozen tumor core biopsy submission (optional study A091105-ST1)**

When safe and feasible, according to the treating investigator and proceduralist obtaining biopsy, consenting patients will undergo 2 biopsies (procuring 5 cores for each biopsy) for correlative study A091105-ST1. Depending on tumor location, biopsies can be obtained at the discretion of surgeon or interventional radiology under image guided CT or Ultrasound. Core biopsies should be performed with either 14 (prefer) or 18 gauge needles. When possible, different areas of the tumor should be biopsied. Each core sample will be transferred to individual cryovials. The cryovials containing the 5 research core biopsy specimens should be immediately immersed in liquid nitrogen for 5 minutes. If liquid nitrogen is not available, the specimen may be immersed in a refrigerated cryobath, available in most surgical pathology frozen section rooms. If using a cryobath, one should be certain that the temperature of the bath is at or below  $-40^{\circ}\text{C}$ . As a last option, specimens may be frozen by complete immersion in an ethanol / dry-ice bath. Specimens should be left in the cryobath or dry ice bath for at least 15 minutes to ensure complete freezing. **Specimens should not be frozen by placing fresh tissue in a  $-70^{\circ}\text{C}$  freezer or inside a cryostat.** Once frozen, tissue may be stored in at least  $-70^{\circ}\text{C}$  mechanical freezer or in dry ice until shipping. Once frozen, take extreme care not to let the tissue specimen thaw. Specimens should be shipped on dry ice within 30 days of collection to Alliance OSU. **For sites that do not have  $-70^{\circ}\text{C}$  freezer**, tissue should be frozen as described above and shipped within 24 hours of collection according to [Section 6.3.6](#).

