### 10.3.4 A091105-ST1 Biopsies

#### Pre- and day 8 (+ 7 days) post-randomization biopsy guidelines

A091105-ST1 must be offered to all patients enrolled on A091105 (although patients may opt to not participate). Patients who consent to A091105-ST1 will undergo 2 biopsies (pre-treatment and day 8 post-randomization).

The following exploratory studies will be performed and analyzed in the laboratory of [name], correlative chair. Bio-informatics analysis will be provided by MSKCC Bio-informatics core lab. Blood, pre-treatment and day 8 matched tumor biopsies are required elements of this study for patients. Patients will undergo 2 biopsies (procuring 5 cores for each biopsy) by interventional radiology under image guided CT or U/S. Core biopsies will be evaluated for the following studies: 1) one core will be formalin fixed for pathological studies and TMA construction, 2) 1 - 2 cores will be used for gene array expression profiling to determine a sorafenib signature of response, whole exome sequencing, microRNA array and epigenetics 3) one core will be used for a constrained evaluation of phospho-proteomic changes utilizing a Zaptosens reverse protein array of selected pathways identified from genetic studies.

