Immunohistochemistry: The polymeric biotin-free horseradish peroxidase method on a Microsystems Bond Max stainer (Beecher Instruments, Bannockburn, IL) will be used for immunohistochemistry. Four-micron-thick sections will be prepared from formalin-fixed paraffin-embedded tissue blocks and dried in a 60-degree oven for 20 minutes. Sections will be placed in the automated Bond Max stainer, pretreated with enzyme-induced epitope retrieval for 2 minutes followed by incubation with antibodies against beta-catenin (BD Biosciences, San Jose, CA), midkine (Antigenix America, NY), MMP2 (Chemicon, MA) and ADAM12 (Abcam, MA). Additional antibodies may be utilized to interrogate specific pathways identified in micro-array work. Anti-mouse secondary antibody and the Refine polymer detection kit (Leica) will be used for immunostaining, with 3,3-diaminobenzidine serving as chromagen. Positive and negative controls will run in parallel. Labeling intensity grading will be performed by soft tissue pathologist ([name]) as none (\_0), weak (\_1), moderate (\_2), or strong (\_3). For the ratio of cellular to nuclear beta catenins, the percentage of positive tumor cells will be estimated from the two paired TMA samples for each case. For nuclear staining, weak (\_1) will be defined functionally as having to view nuclei at X400 to confirm nuclear accumulation. Moderate (\_2) staining could be viewed at X200 and the blue hematoxylin nuclear counterstain. In strong (\_3) staining, the nuclear counterstain will no longer be visible in the majority of nuclei. The staining on the entire array will be performed in the MSKCC clinical immunohistochemistry facility on two occasions and each scored independently.

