Statistics for Core #3 and 4: For each paired sample, differences in protein levels will be compared by paired t-test. This sample size of 75 patients will allow 93% power to detect 1 standardized difference. Quantitative changes in IHC score of VEGF, PDGFR and  $\beta$ -catenin cytoplasm/nuclear ratio will be correlated with disease status at 1 year by Fishers exact test.

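### Section 6.3.2 freezes all five research cores, so the formalin-fixed core that Section 10.3.4 needs for paired histology and immunohistochemistry is never produced

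*Combined protocol and SAP*

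**What the plan says.** Section 6.3.2 is the collection instruction for research cores. It provides that, when safe and feasible, "consenting patients will undergo 2 biopsies (procuring 5 cores for each biopsy) for correlative study A091105-ST1". It continues: "Each core sample will be transferred to individual cryovials". It then directs: "The cryovials containing the 5 research core biopsy specimens should be immediately immersed in liquid nitrogen for 5 minutes". A cryobath or an ethanol/dry-ice bath is allowed where liquid nitrogen is unavailable, and storage and shipping are frozen throughout. The section warns: "Once frozen, take extreme care not to let the tissue specimen thaw". It contains no formalin step.

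Section 10.3.4 sets out what the cores are for. Its opening list says that "one core will be formalin fixed for pathological studies and TMA construction". Under Core #5, the planned readings are Ki-67 (before treatment and after therapy), fibrosis, vascularity, necrosis and the beta-catenin ratio. For the staining itself, "Four-micron-thick sections will be prepared from formalin-fixed paraffin-embedded tissue blocks".

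Section 15.3.3 plans a statistical use of staining change. The sentence begins "Quantitative changes in IHC score of VEGF, PDGFR and", goes on to the beta-catenin cytoplasm/nuclear ratio, and relates these changes to disease status at 1 year by Fisher's exact test.

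**The concern.** Sites collect tissue from Section 6.3, not from the laboratory plan. A site that follows Section 6.3.2 exactly sends ten frozen cores per patient and no fixed one. The laboratory plan then calls for a fixed core that it has not been sent.

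Histology is part of a stated aim: Sections 2.3.2 and 10.3.1 both list it first among the ways in which treatment-induced change will be measured in paired biopsies. At stake are the within-patient comparison of pre-treatment and day 8 morphology and staining, and any analysis in Section 15.3.3 that relies on it.

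**Working it through.** The plan gives no sample size or power figure for this analysis, so there is none to reproduce. The check is a core count and a comparison of sections.

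1. **Supply per biopsy (Section 6.3.2).** Cores taken: 5. Cores frozen: 5. Left for formalin: 5 − 5 = 0.

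2. **Demand per biopsy (Section 10.3.4).** The core headings assign 2 to nucleic acids, 2 to protein and 1 to histology and staining: 2 + 2 + 1 = 5. The opening list of the same section adds up differently, 1 fixed + 1 to 2 for nucleic acids + 1 for protein = 3 to 4. Both counts include exactly one fixed core.

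3. **Shortfall.** One fixed core is required and none supplied at each time point. Per patient: 2 × 1 = 2 required, 2 × 0 = 0 supplied.

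4. **Other sources of fixed tissue.** Section 6.3.1 gives instructions for formalin-fixed tissue, but only for the archival block. The table in Section 6.3 schedules that block at baseline only, whereas the research biopsy is scheduled at baseline and Cycle 1 Day 8. The block therefore cannot supply the day 8 member of a pair. Section 6.3.5 names research tumor material only as frozen tubes and asks for no core number on the label.

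5. **Later fixation.** No section tells the biorepository or the laboratory to thaw and fix a frozen core, or to stain frozen sections.

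6. **Does freezing four cores suffice?** By the core headings, the frozen assays need 2 + 2 = 4, so 5 − 4 = 1 core can be fixed with none in reserve. By the opening list they need 2 to 3, which would leave 1 or 2 spare.

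7. **Link to Section 15.3.3.** The staining-change sentence stands under the statistics for Cores #3 and 4, the protein cores, and not under Core #5. It names VEGF, PDGFR and beta-catenin. The antibodies named in the Core #5 text are beta-catenin, midkine, MMP2 and ADAM12, with others only as a possibility. The overlap is one marker, beta-catenin. VEGFR2/3 and PDGFR-beta do appear in Section 10.3.4, but as protein-array targets on Cores #3 and #4.

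**The case against.** The best reply is that Section 10.3.4 describes laboratory work in the passive voice. It does not say that the site fixes the core, so sites might freeze and ship everything and the laboratory might then fix one core on receipt. On that reading the thaw warning governs only storage and shipping. This shows that fixing or staining frozen tissue may be technically possible, and the documents do not call such tissue unusable. But no such step is written anywhere, it sits badly with the warning, and the staining method is specified for paraffin sections. The objection rules out saying that the analysis is impossible; it does not rescue the method as written.

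Three stronger inferences are tempting, and the documents do not support them.

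- **All tissue-microarray work is lost.** Section 15.3.3 groups microarray studies with archival paraffin tissue. Every patient must submit an archival block, and for consenting patients Section 6.3.1 also assigns it to this substudy. Baseline microarray work can proceed.
- **The whole staining-change analysis in Section 15.3.3 falls with Core #5.** That sentence is filed under other cores and shares only beta-catenin with the named Core #5 panel, so the link is partial.
- **Patients had two biopsies to no purpose.** The expression array, exome, microRNA and protein assays use frozen tissue and account for four of the five cores.

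It can also be said that an amendment comes too late. The current text post-dates the unblinding of November 17, 2017 (Section 15.1), cores are taken only at baseline and Cycle 1 Day 8, and Section 7.0 does not require them after crossover. Few or no new biopsies may remain, although the documents do not say so outright. This bears on which part of the remedy matters, not on whether the conflict exists.

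**Conclusion.** The conflict is real and follows from the text alone. As written, 0 of 5 cores per biopsy are formalin-fixed against 1 required, and the paired pre-treatment/day 8 histology, Ki-67 and beta-catenin staining on paraffin sections cannot be done by the stated method.

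The conclusion assumes that sites followed Section 6.3.2 and that no instruction outside these documents, such as a laboratory manual, supplied the missing step. If sites fixed a core on their own initiative, some paired material exists, but which patients have it would depend on local practice.

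The scope is narrow: one part of an optional, exploratory substudy. Archival CTNNB1 sequencing, archival microarray work, the frozen assays and the clinical endpoints stand. The 93% power statement in Section 15.3.3 refers to paired protein levels on Cores #3 and 4 and is not touched by this point. A correction is still warranted, because a stated collection rule defeats a stated use of the tissue.

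**What to change.** **For any biopsy still to be taken.** Amend Section 6.3.2 so that one of the five cores goes directly into formalin and four are frozen. Number the cores to match Section 10.3.4, and add the core number and the fixed specimen to the labelling and shipping text. Settle the opening list of Section 10.3.4 against its core headings (3 to 4 cores versus 5). The cost is wording only, with no extra core or procedure. The downside is that, by the core headings, no spare frozen core remains.

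**For cores already collected.** This is probably the part with practical effect. Establish from biorepository and laboratory records how the cores were handled, and report how many patients have a usable fixed pair. Then amend Section 15.3.3 in one of two ways: drop the paired staining-change analysis, or state that it uses frozen-derived tissue and analyse it separately from any paraffin results. Pooling the two would mix fixation method with treatment effect if the methods differ between time points.

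**In either case.** Reconcile the staining-change sentence in Section 15.3.3 with Core #5: which core it draws on, which markers it covers, and whether VEGF and PDGFR are to be stained or read from the protein array. This costs a short amendment and a check of specimen records.
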